7.2 Definition for Analysis Populations

The ITT population will consist of all randomized subjects.

All efficacy analyses will be performed using the mITT population, consisting of all randomized subjects who received at least 1 dose of study drug, had an evaluable baseline period of eDiary data and had at least 1 evaluable post-baseline 4-week period (Weeks 1 to 4, 5 to 8, and 9 to 12) of eDiary data. For efficacy analyses, data will be analyzed according to subjects' randomization assignments, regardless of actual treatment received.

All safety analyses will be performed using the safety population, consisting of all subjects who received at least 1 dose of study drug during the double-blind treatment period. The safety population in the active treatment extension period consists of all subjects who received at least 1 dose of study drug during the active treatment extension period. For safety data analyses, the subjects will be analyzed according to actual treatment received (rather than as randomized).

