Summary and Analysis of the Primary Endpoint

The primary efficacy endpoint is the change from baseline in mean monthly migraine days across the 12-week double-blind treatment period. To test the primary hypotheses that each dose of atogepant is

superior to placebo for the primary endpoint, the change from baseline in monthly migraine days at each monthly period will be analyzed using a MMRM with treatment group, visit, prior exposure (yes/no) to a migraine prevention medication with proven efficacy, and treatment group-by-visit interaction as categorical fixed effects. It will also include the baseline score and baseline-by-visit interaction as covariates. An unstructured covariance matrix will be used to model the covariance of within-subject repeated measurements. The Kenward-Roger¹¹ approximation will be used to estimate the denominator degrees of freedom. The analysis will be performed based on all postbaseline values using only the observed cases without imputation of missing values.

Pairwise contrasts in the MMRM model will be used to make the pairwise comparisons of each atogepant dose to placebo.

Copy-reference approach as 1 sensitivity analysis will be performed on the primary endpoint to assess the robustness of the MMRM analysis to possible violation of the MAR assumption. This sensitivity analysis is one type of PMM, under which data could be MNAR, with repeated analyses combined via the reference-based MI procedure. Subjects who discontinued in the atogepant groups are assumed to have no treatment effect after the discontinuation. Subjects are assumed to copy the profile of placebo arm and missing values are imputed based on the distribution estimated from the placebo group under the MAR using copy reference approach. An additional sensitivity analysis, MI in conjunction with robust regression, will be performed in case of non-normality for the primary efficacy endpoint.

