7.7 Overall Type I Error Control

The Hochberg procedure¹² will be used to control the overall Type I error rate at a 0.05 level (2-sided) for multiple comparisons of each atogepant dose with placebo for the primary endpoint. Detailed procedure is provided below.

Let $p_{(1)}$, $p_{(2)}$, and $p_{(3)}$ denote the nominal p-values in increasing order from the 3 comparisons of atogepant doses versus placebo.

- Step 1: If $p_{(3)}$ is ≤ 0.05 , then all the 3 comparisons are considered statistically significant at the 2-sided significance level of 0.05 and stop here; otherwise, go to Step 2.
- Step 2: If $p_{(2)}$ is ≤ 0.025 , then the corresponding 2 comparisons for $p_{(2)}$ and $p_{(1)}$ are considered statistically significant at the 2-sided significance level of 0.05 and stop here; otherwise, go to Step 3.
- Step 3: If $p_{(1)}$ is ≤ 0.01667 , then the corresponding comparison for $p_{(1)}$ is considered statistically significant at the 2-sided significance level of 0.05; otherwise, stop here.

Adjusted p-values using Hochberg procedure will also be provided.

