9.3.3 Sensitivity and Supplementary Analyses of the Primary Efficacy Endpoint

The sensitivity analyses for missing data handling will be conducted and summarized in this section based on the mITT Population.

ANCOVA Model Based on 3-month Average of the Monthly Migraine Days

A supportive analysis will be performed on the primary endpoint using an ANCOVA model. The response variable for the ANCOVA model is the change from baseline in the

calculated average monthly migraine days during the 12-week double-blind treatment period for each participant. The ANCOVA model includes fixed effects for treatment, prior exposure (yes/no) to a migraine prevention medication with proven efficacy, and baseline score. The treatment difference for atogepant dose versus placebo will be estimated and reported along with the corresponding 95% CI and nominal p-value for superiority testing.

Copy-Reference Approach

Copy-reference approach is one type of pattern-mixture models (PMM), under which data could be missing-not-at-random (MNAR), with repeated analyses combined via the reference based multiple imputation (MI) procedure.⁷ This approach is to assess the robustness of the MMRM analysis to possible violation of the missing-at-random (MAR) assumption in the primary analysis.

Step 1. A few intermittent missing values will be imputed by the Markov Chain Monte Carlo (MCMC) first. The MCMC imputation assumes missing-at-random (MAR) for intermittent missing data. The MCMC method will be implemented using SAS Proc MI statement "MCMC impute monotone." This is achieved using the option IMPUTE MONOTONE in the MCMC statement. Then the rest of the missing data will follow a monotone missing pattern.

Step 2. Implementation of the copy reference method are as follows:

- The reference-based approach uses the placebo group as the reference. The missing values in the reference group are imputed using the observed data in that group under the missing-at-random assumption. The missing pattern is defined by the subject's last visit with a non-missing value. The mean vector and the covariance matrix of the multivariate normal distribution are estimated for the reference group. The imputation of missing data is not based on each of the reasons for early termination, because there may not be enough non-missing efficacy data in each of the reason categories to serve as a stable reference.

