- For atogepant treatment groups, missing values are imputed based on the distribution estimated from the reference group (placebo group).

The first PROC MI will be performed 100 times using MCMC method for partial imputation of the data with a non-monotone missing pattern. The output dataset will then be used as the input dataset for the next PROC MI. Note that the output dataset already contains 100 copies of the original dataset. With the next invocation of MI procedure, the missing data will be filled in (Step 1 and 2) for the existing copies. This is achieved with the use of NIMPUTE 1 and a BY Imputation statement. Finally, each of the 100 imputed datasets will be analyzed using an analysis of covariance (ANCOVA) model. For a given imputed dataset, the average change from baseline in monthly migraine days is calculated across the 3 post-baseline months and is used as the response variable in the model. The model includes treatment group as a fixed factor, baseline monthly migraine days and prior exposure (yes/no) to a migraine prevention medication with proven efficacy as covariates. The LS mean difference and corresponding SE is estimated from the model comparing each atogepant treatment group with the placebo group.

The ANCOVA analysis results from 100 completed datasets are combined for overall estimation and inference using Rubin's rule⁸ to produce a pooled estimate of LS mean difference, its SE, and corresponding p-value for the test of null hypothesis of no treatment effect.

Sensitivity Analysis for Possible Violation of Normality Assumption

An additional sensitivity analysis, MI in conjunction with robust regression, will be performed in case of non-normality for the primary efficacy endpoint. This method has been described and referred to as ADAP [R] in Mehrotra et al. 2012.⁹ The details of the method are as follows.

The normality test is performed on the residuals which are generated by the same MMRM as used for the primary efficacy analysis. The residuals are scaled by the inverse Cholesky root of its estimated variance-covariance matrix. The Kolmogorov-Smirnov test for

normality is applied to the de-correlated and scaled residuals and normality test is rejected if p-value from the Kolmogorov-Smirnov test is less than 0.01.

If the normality test is rejected, sensitivity analysis below will be performed:

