1. Create complete datasets using MI based on the Markov Chain Monte Carlo (MCMC) approach. Imputed data will consist of 100 complete datasets.
2. Each of the 100 complete datasets will be analyzed using robust regression (M-estimation) to protect against either observed outliers in the original incomplete dataset, or imputed outliers in the completed datasets. For a given complete dataset, the average change from baseline in monthly migraine days is calculated across the 3 post-baseline months and is used as the response variable in the robust regression model. The model includes treatment group, prior exposure (yes/no) to a migraine prevention medication with proven efficacy as fixed factors, and baseline score. The mean difference and corresponding SE are estimated from the model comparing each atogepant treatment group with the placebo group.

The robust analysis results from 100 completed datasets are combined for overall estimation and inference using Rubin's rule⁸ to produce a pooled estimate of treatment difference, its SE, and corresponding p-value for the test of null hypothesis of no treatment effect.

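### Protocol 7.4 says atogepant dropouts have no treatment effect after discontinuation, but copy reference carries part of their observed benefit forward; at the planned dropout the difference is small

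*Protocol*

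**What the plan says.** Protocol 7.4 offers copy reference as the check on the missing-at-random (MAR) assumption behind the primary mixed model for repeated measures. It gives the assumption in two consecutive sentences. The first is "Subjects who discontinued in the atogepant groups are assumed to have no treatment effect after the discontinuation". The second says "Subjects are assumed to copy the profile of placebo arm and missing values are imputed based on the distribution estimated from the placebo group", and names copy reference as the approach.

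SAP 9.3.3 gives the steps. Intermittent gaps are filled first under MAR, which leaves a monotone pattern. Then "The mean vector and the covariance matrix of the multivariate normal distribution are estimated for the reference group", and missing values in the atogepant arms are drawn from that placebo-based distribution. On patterns it says "The missing pattern is defined by the subject's last visit with a non-missing value". Each of the 100 completed datasets is analysed by ANCOVA on the three-month average, and the results are pooled by Rubin's rule. The SAP does not repeat the no-effect sentence.

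The analysis set matters too. Under Protocol 7.2 a subject is in the mITT population only if he or she "had at least 1 evaluable post-baseline 4-week period (Weeks 1 to 4, 5 to 8, and 9 to 12) of eDiary data".

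**The concern.** The two protocol sentences describe different assumptions. Copy reference treats a dropout as if he or she had been a placebo subject throughout, and predicts the missing months from the subject's own observed months. An atogepant subject who did better than placebo while on drug looks like a placebo subject with a favourable deviation, and the within-subject correlation projects that deviation forward. The imputed months therefore still contain some treatment effect. Because of the mITT rule, every dropout in this analysis has at least one observed month to project from.

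An assumption of no effect after discontinuation corresponds to jump to reference. There the deviation is measured from the subject's own arm mean, while the expected level moves to the placebo mean.

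No other planned analysis fills the gap. The mixed model assumes MAR, and the supportive ANCOVA averages the available months. The robust-regression analysis starts from "Create complete datasets using MI based on the Markov Chain Monte Carlo (MCMC) approach", addresses non-normality, and runs only if the normality test is rejected. No tipping-point, delta-adjusted or jump-to-reference analysis is planned. A reader of Protocol 7.4 would credit the trial with a harsher test than the one it runs.

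**Working it through.** **Inputs from the documents (Protocol 7.8, Table 2; SAP 2.4, Table 1).** Assumed differences from placebo are 1.7, 1.38 and 1.21 days for 60, 30 and 10 mg. The SD is 3, with 130 randomized and 123 effective subjects per arm (130 × (1 − 0.054) = 122.98) and 5.4% dropout. The test is two-sided at 0.05 with the Hochberg procedure over three doses.

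**Inputs assumed.** Correlation between months ρ from 0.3 to 0.8, which neither document gives; the same effect in each month; dropouts who had their arm's average benefit while observed.

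**Reproducing the plan's figures.** A simulation of 1,000,000 trials with a shared placebo arm gives Hochberg-adjusted power of 0.987, 0.938 and 0.878 for 60, 30 and 10 mg, and 0.993 for at least one dose. The plan states 0.986, 0.937, 0.877 and 0.992. The planning inputs are read correctly.

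**Share of the effect retained.** The SAP does not write out the conditional step; it follows from the named method. The expected imputed value is the placebo mean plus B × (own observed months − placebo means), with B taken from the placebo covariance. If the observed months lie below placebo by the effect δ, the imputed month lies below placebo by (sum of B) × δ. Under equal correlation:
- last observed month 1: retained share = ρ
- last observed month 2: retained share = 2ρ/(1 + ρ)

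An imputation run with 200,000 subjects per arm at ρ = 0.7 and δ = 1.21 left about 0.85 days (70%) and 0.99 days (82%), matching the formulas.

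**Share of the penalty applied.** Leaving after month 1 loses two of three months; leaving after month 2 loses one. With dropout split evenly, removing all effect costs δ × d × (½ × 2/3 + ½ × 1/3) = 0.5δd, where d is the dropout rate. Copy reference costs δ × d × [(1/3)(1 − ρ) + (1/6)(1 − ρ)/(1 + ρ)]. The ratio is (2/3)(1 − ρ) + (1/3)(1 − ρ)/(1 + ρ).

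For 10 mg at d = 0.054, the no-effect penalty is 0.5 × 1.21 × 0.054 = 0.033, so the no-effect estimate is 1.177.

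| ρ | Retained after month 1 | Retained after month 2 | Penalty applied | 10 mg, copy reference | Gap from 1.177 (days) |
|---|---|---|---|---|---|
| 0.3 | 30% | 46% | 65% | 1.189 | 0.012 |
| 0.5 | 50% | 67% | 44% | 1.195 | 0.018 |
| 0.7 | 70% | 82% | 26% | 1.202 | 0.024 |
| 0.8 | 80% | 89% | 17% | 1.204 | 0.027 |

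**Largest gap at 5.4% dropout.** For 60 mg with all dropout after month 1 and ρ = 0.8, the no-effect penalty is 1.7 × 0.054 × 2/3 = 0.061 and copy reference applies 20% of it, 0.012. The gap is 0.049 days.

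**Scale.** The standard error of a difference is about 3 × √(2/123) = 0.38 days, so 0.02 days is about 5% of it and 0.049 days about 13%. With all dropout after month 1 and ρ = 0.7, Hochberg power for 10 mg is 0.878 under MAR, 0.870 under copy reference and 0.851 under no effect, holding SD 3 and n = 123.

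**Higher dropout (assumed 20%, all after month 1, ρ = 0.7).** The 10 mg difference is 1.162 under copy reference and 1.049 under no effect; unadjusted power is 0.859 and 0.783.

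**Another correlation shape.** If correlation decays with distance (first-order autoregressive), the retained share after month 1 averages (ρ + ρ²)/2 and after month 2 is ρ. At ρ = 0.5 that is 38% and 50%, lower than under equal correlation.

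**The case against.** The strongest reply is that this is one loose sentence. The next sentence names the method, Protocol 7.4 defers detail to the SAP, and the SAP specifies copy reference coherently. A programmer would not be misled. Nothing in the documents requires jump to reference, and copy reference is a legitimate departure from MAR.

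The size is also small, and 5.4% probably overstates the number of subjects imputed. Those who leave without an evaluable month are outside the mITT population. Those who leave in month 3 with at least 14 diary days are prorated and have no missing month. The carry-over is proportional to the benefit each dropout actually showed; someone who left without responding carries nothing forward. Covariates in the imputation model, which the SAP does not list, would lower the relevant correlation.

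All of that stands on size. It also rules out a reading that is tempting here: that dropouts keep most of their benefit. Under equal correlation this needs ρ above 0.5 when month 1 is the last observed, or above 1/3 when month 2 is. The documents give no correlation, so they do not establish it. Nor can any single figure for the share of the penalty applied be quoted without its ρ.

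The reply does not rescue the sentence. Following the placebo distribution given one's own history is a defensible assumption, but it is not an assumption of no effect.

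**Conclusion.** Protocol 7.4 states an assumption that the specified analysis does not impose, and no other planned analysis imposes it. The size in the brief rests on equal correlation, average benefit before dropout, a constant effect over months and, for the 65% to 17% range, dropout split evenly between months 1 and 2.

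A reader might infer that the primary result is left unprotected against informative dropout. The planning figures do not support that: at 5.4% dropout the two assumptions differ by a small fraction of a standard error and, in the case computed for 10 mg, by about 2 points of power. The difference would matter mainly if dropout were much higher than planned, and that is when a sensitivity analysis is most needed.

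**What to change.** Before the double-blind database lock:

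1. Keep copy reference, and add to SAP 9.3.3 a jump-to-reference analysis for months missing after discontinuation, with the same 100 imputations, ANCOVA and Rubin's rule. Identify it as the analysis that imposes no effect after discontinuation. Because the SAP groups subjects by last non-missing visit and not by discontinuation, state which missing months it covers.
2. Reword Protocol 7.4 to say that copy reference imputes from the placebo distribution given the subject's own earlier values.
3. If jump to reference is not added, the no-treatment-effect sentence must be removed.

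The cost is a little programming, two short text changes and a slightly less favourable sensitivity estimate. The primary analysis and its type I error control are unaffected.

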7.5 Statistical Analyses for Safety

All safety analyses will be performed using the safety population.

The safety parameters will include AEs, clinical laboratory evaluations, vital sign measurements, ECG parameters, and the C-SSRS. For each of the clinical laboratory, vital sign, and ECG parameters, the last non-missing safety assessment before the first dose of treatment will be used as the baseline for all analyses of that safety parameter.

Continuous variables will be summarized by the number of subjects, and mean, SD, median, minimum, and maximum values. Categorical variables will be summarized by number and percentage of subjects.

Descriptive statistics for safety endpoints will be provided by treatment period (double-blind treatment period or active treatment extension period). For selected safety endpoints, analyses will be provided across both treatment periods (double-blind and active treatment extension periods) to show the trend over time. Details will be specified in the SAP.

7.6 Interim Analysis

No interim analysis of efficacy data is planned for this study.

7.7 Overall Type I Error Control

The Hochberg procedure¹² will be used to control the overall Type I error rate at a 0.05 level (2-sided) for multiple comparisons of each atogepant dose with placebo for the primary endpoint. Detailed procedure is provided below.

Let $p_{(1)}$, $p_{(2)}$, and $p_{(3)}$ denote the nominal p-values in increasing order from the 3 comparisons of atogepant doses versus placebo.

- Step 1: If $p_{(3)}$ is ≤ 0.05 , then all the 3 comparisons are considered statistically significant at the 2-sided significance level of 0.05 and stop here; otherwise, go to Step 2.
- Step 2: If $p_{(2)}$ is ≤ 0.025 , then the corresponding 2 comparisons for $p_{(2)}$ and $p_{(1)}$ are considered statistically significant at the 2-sided significance level of 0.05 and stop here; otherwise, go to Step 3.
- Step 3: If $p_{(1)}$ is ≤ 0.01667 , then the corresponding comparison for $p_{(1)}$ is considered statistically significant at the 2-sided significance level of 0.05; otherwise, stop here.

Adjusted p-values using Hochberg procedure will also be provided.

7.8 Sample Size Determination

Approximately 520 subjects will be randomized to one of the 4 treatment groups (placebo, atogepant 10 mg once daily, atogepant 30 mg once daily, atogepant 60 mg once daily) in a 1:1:1:1 ratio.

A sample size of 130 subjects per treatment group provides approximately 88%, 94% or 99% power to show statistically significant improvement between each of the 3 atogepant doses (10 mg, 30 mg, or 60 mg) and placebo for the primary efficacy endpoint, respectively, on the mITT analysis set. Assumptions in this sample size calculation are based on the ADVANCE study in a US adult population.¹³

The assumed treatment difference between each atogepant dose versus placebo and the standard deviation for the primary endpoint are shown in [Table 2](#). The dropout rate is assumed to be approximately 5.4% for the double-blind treatment period because the observed dropout rate was less than 5% for trials conducted in Japanese patients with EMs.¹⁴⁻¹⁷ All statistical powers presented in this section were calculated adjusting for multiple comparisons using the Hochberg procedure with the family-wise Type I error rate being controlled at a 0.05 level (2-sided).

Table 2. Power and Sample Size Calculations for the Endpoint, Change from Baseline in Monthly Migraine Days Across the 12-Week Treatment Period

Randomized n/arm	Effective n/arm	Treatment Arm	Treatment Difference	Standard Deviation	Power for individual Dose	Probability (At Least one arm is significant)
130	123	60 mg	1.7	3	0.986	0.992
		30 mg	1.38	3	0.937	
		10 mg	1.21	3	0.877	

8 ETHICS

8.1 Independent Ethics Committee/Institutional Review Board

The protocol, informed consent form(s), recruitment materials, and all subject materials will be submitted to the IEC/IRB for review and approval. Approval of both the protocol and the informed consent form(s) must be obtained before any subject is enrolled. Any amendment to the protocol will require review and approval by the IEC/IRB before the changes are implemented to the study. In addition, all changes to the consent form(s) will be IEC/IRB approved.

8.2 Ethical Conduct of the Study

The study will be conducted in accordance with the protocol, Operations Manual, ICH guidelines, applicable regulations, and guidelines governing clinical study conduct and the ethical principles that have their origin in the Declaration of Helsinki. Responsibilities of the investigator are specified in [Appendix B](#).

8.3 Subject Confidentiality

To protect subjects' confidentiality, all subjects and their associated samples will be assigned numerical study identifiers or "codes." No identifiable information will be provided to AbbVie.

